1. INTODUCTION

1.1 INTRODUCTION WITH LITERATURE REVIEW

Upper back refers to the region anywhere between cervical regions to thoracic region. Pain in this region referred as upper back pain. According to the available literature, there is no any clear definition for upper back pain. In some literature it often referred as thoracic back pain(Fouquet *et al.*, 2015). Thoracic back pain has to consider as a serious issue than neck and low back pain because vital organs such as heart and lungs belong to its anatomical land mark. Thoracic spine mobility affects the mobility of rib cage, stiffness in the thoracic spine reduce the effectiveness of respiratory mechanism.

Thoracic pain mainly occurs due poor posture and overuse injuries. Long term sitting with bad posture leads to the tightness chest muscles mainly pectoralis major, minor, subclavius and intercostals, lead to hunched position, while the muscles of the upper back and neck mainly trapezius, rhomboids, levator scapulae, splenius and erector spinae become weak (Lin *et al.*, 2020). These imbalances can lead to tension and pain. Long term screening which includes smartphone and laptop usage exaggerating this condition among young population (Shete and Shah, 2019; Puntumetakul *et al.*, 2022). In addition to that, mental health factors like academic and personal stressors and physical inactivity significantly influence this condition among high school or undergraduate students (Shan *et al.*, 2013). Further, it was increased after the COVID-19 pandemic (Amro *et al.*, 2020; Leirós-Rodríguez *et al.*, 2020; Akulwar-Tajane *et al.*, 2021; Elghomati *et al.*, 2022).

Generally, Prevalence of acute or subacute thoracic back pain and chronic pain is ranging from 3.4%- 34.8% and 15.6%- 19.5% respectively among general population (Fouquet *et al.*, 2015). Prevalence of Upper back pain among high school students is high, a study conducted among Finnish high school students depicts 17% reported disturbing symptoms in the neck, upper back and shoulder (Niemi *et al.*, 1997). Further a study conducted in Saudi Arabia among undergraduates who are following dentistry complained about neck pain (69.2%) followed by shoulder (67.1%) and upper back pain (46.9%)(Felemban *et al.*, 2021).

A systematic review on “The effectiveness of non-invasive interventions for musculoskeletal thoracic spine and chest wall pain” depicts about lack of quality studies regarding no physical therapy management regarding musculoskeletal thoracic pain. Further, this study shows that, multimodal program includes manual therapy, heat or advice and exercise clinically not important pain reduction like spinal manipulation (Southerst *et al.*, 2015).

Thoracic Spinal mobilization technique forwarded by Maitland suggests that Grade I and II oscillatory technique mainly contributes in reduction of pain can potentially help reduce pain in the spine through several mechanisms including gate control theory, by release of endorphins, and improve blood flow to the muscle and Grade III and Grade IV techniques mainly contributes in improving mobility (Lee and Lee, 2017). Application of Maitland’s mobilization technique grades will be differ according to the patient’s individual factors and pain intensity. In addition, Myofascial release therapy is a type of gentle, constant massage that releases tightness and pain throughout your myofascial tissues. Few literature forwarded that pressure or tension should be applied for nearly 40 to 120 seconds in an angle of 30- 60 degree for the effective release of trigger points(Kim, Sung and Lee, 2017). Application of pressure increases the blood flow and removal of potential waste product from the specific muscle. It will cause the pain reduction. Furthermore, Thoracic mobility exercises are found to be very significant in mobility of the spine and improve the muscle strength of thoracic extensors which mainly includes Cat and Camel exercises, Horizontal chest expansion and cross arm chest expansion (Cho, Lee and Lee, 2017). It aims to enhance the flexibility, strength, and alignment of the spine, while the incorporation of controlled breathing can further aid in relaxation, stress reduction, and improved movement patterns(Csepregi *et al.*, 2022).

Prevalence of musculoskeletal pain among undergraduates in Sri Lanka depicts a significant increase after the COVID-19 due to increase screen time, sitting in long time lecture hours for nearly seven hours and increase of academic work load (Patterson and Warnakulasuriya, 2022). It act as a vicious cycle in increase upper back pain among undergraduates. Proper ergonomic guidance and exercises will be possible solutions for this specific pain. Further, it will help to improve the academic performance among undergraduates and to achieve their future endeavour. In addition, availability of research regarding upper back pain prevalence and physiotherapy treatment is very low.

Proper evidence regarding treatment of upper back pain is very important due to increase of screening and stress day by day. In clinical settings, thoracic mobility exercise combination with breathing depicts a significant improvement in upper back pain rather than manual therapy. As a researcher, effectiveness of both therapies should be checked scientifically.

1.2 OBJECTIVES

General Objective:

To find out the effectiveness thoracic mobility exercise compared with manual release technique in minimizing upper back pain

Specific Objective:

- To evaluate correlation between the sociodemographic factors and pain intensity of participants in experimental and control group.
- To evaluate the effectiveness of thoracic mobility exercise and manual release technique in improving upper back pain intensity
- To evaluate the effectiveness of thoracic mobility exercise and manual release technique in improving upper thoracic mobility
- To evaluate the effectiveness of thoracic mobility exercise and manual release technique in improving trunk upper back muscle strength
- To evaluate the effectiveness of thoracic mobility exercise and manual release technique in improving disability

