Alternate Hypothesis: $H_1: \mu_1 - \mu_2 \neq 0$

There is a difference in muscle strength of spinal extensors of participants between experimental and control group

5. Hypothesis about differences in disability of participants between control group and experimental group.

Null Hypothesis: $H_0: \mu_1 - \mu_2 = 0$

There is no difference in disability of participants between experimental and control group.

Alternate Hypothesis: $H1: \mu_1 - \mu_2 \neq 0$

There is a difference in disability of participants between experimental and control group.

2.6 Sample Size:

Sample size is Calculated by using G*power 3.1.9.4 software by assigning power 80% effective size 0.5, type I error = 0.05 and type II error = 0.2. Therefore calculated sample size was 42. Drop down rate of participants is assigned as 25 %. Therefore final sample size which obtained is 60 (Kang, 2021).

2.7 Sampling method:

Simple Random Sampling will be used as sampling technique as well as 30 Participants will be randomly allocated to each group. Participant will be allocated to the groups by using lottery method.

2.8 Data collection:

Undergraduates who are having upper back pain more than 7 days will be selected as sample and those who are having any contraindications, recent surgeries, fractures, accidents will be excluded from the students. Informed consent will be obtained from the participants. Participants will be allocated to one group by blindly select the number by lottery method. Thirty participants will be allocated randomly to each group. Allocation was concealed. Assessors will not be aware of intervention or control group and collect the demographic data, Pain assessment, Range of Motion and muscle strength at the baseline and after two weeks of intervention.

2.9 Data collection tool:

Measurement tool contains two sections such as pre-test and post-test questionnaire. In Pre-test questionnaire, there are six sections which includes personal details of the participants, pain related questions, Measurement of range of motion at base line, muscle strength at base line and pain-self-efficacy Questionnaire (PSEQ) at base line. In Post-test questionnaire, there are 4 sections which include, pain related questions

mainly pain intensity after two weeks, muscle strength after two weeks, Range of motion after two weeks and pain-self-efficacy Questionnaire (PSEQ).

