Personal details of the participants will be collected separately for the concealed allocation and participants will be identified by code number. Participants' age, gender, height, weight, BMI, family size, bread winner of the family, monthly income and financial support for the study will be collected in the demographic data section. In third section, questions related to occurrence of pain, pain duration and treatments which were undertaken for the pain will be collected from the participants.

VAS scale will be used to measure the intensity of pain in different situations which include present pain intensity, in sitting, in forward bending, in standing, in walking, in sleeping, in transferring and during day to day activities. Visual Analogue Scale will be used to measure the pain intensity. Subjects will be asked to mark the number between 0 and 10 that fits best to their pain intensity. Zero indicates 'no pain at all' whereas 10 represents 'the worst pain ever possible' (Figure 1). Measurement will be obtained in the baseline and at the end of two weeks.

[figure not shown]

Figure 1- VAS Scale

Thoraco-Lumbar flexion and Extension of thoracic spine Range of Motion will be taken in the fourth section. Measurement will be taken by using measuring tape. Measurement will be taken at the baseline and after two weeks. In the fourth section, muscle strength of thoracic spine extensors will be measured using Oxford-Grading Scale. Measurement will be taken at the baseline and after two weeks. The Oxford Muscle Scale is a numerical rating scale used to quantify the power or strength produced by the contraction of a muscle. The scale was originally developed by a UK government research group called the Medical Research Council (MRC). Reliability of the scale

explained by Intraclass Correlation Coefficient (ICC) and Interrator Reliability. It shows high ICC coefficient of 0.95 (ranging from 0.92 to 0.97) (Hermans et al., 2012).

Muscle Strength Grading Scale (Oxford Scale)	
0/5	No Contraction
1/5	Visible/palpable muscle contraction but no movement
2/5	Movement with gravity eliminated
3/5	Movement against gravity only
4/5	Movement against gravity with some resistance
5/5	Movement against gravity with full resistance

Table 1

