In the sixth section, The Pain Self-Efficacy Questionnaire (PSEQ) is a 10-item questionnaire developed to assess the confidence people with ongoing pain have in performing activities while in pain. The PSEQ has high internal consistency (0.92 Cronbach's alpha) and test-retest reliability is high of a 3-month period.

	0 "not at all confident"	1	2	3	4	5	6 "completely confident"
1. I can enjoy things, despite the pain.							
2. I can do most of the household chores (e.g. tidying-up, washing dishes, etc.), despite the pain.							
3. I can socialise with my friends or family members as often as I used to do, despite the pain.							

4. I can cope with my pain in most situations.						
5. I can do some form of work, despite the pain. ('work' includes housework, paid and unpaid work).						
6. I can still do many of the things I enjoy doing, such as hobbies or leisure activity, despite pain.						
7. I can cope with my pain without medication.						
8. I can still accomplish most of my goals in life, despite the pain.						
9. I can live a normal lifestyle, despite the pain.						
10. I can gradually become more active, despite the pain.						

Table 2

2.10 Ethical Considerations:

Ethical approval will be obtained from the Institutional Review Board of Bangladesh Health Professional Institute. Written informed consent will be obtained from all the subjects who are willing to participate in the study. Participation in this research is entirely voluntary basis and the participants have the right to withdraw from the study at any time.

2.11 Outcome measures:

Baseline outcome measures are demographic characteristics of participants such as age, gender, BMI, family size, bread winner of the family, monthly income and financial

support for study; Pain duration; Pain intensity at present moment, sitting, forward bending, standing, walking, sleeping, transferring and pain when performing day to day activities; Range of Motion of thoraco-lumbar flexion and extension; Muscle strength of thoracic spine extensors and overall scale of Pain-Self- efficacy Questionnaire. After two weeks same outcome measures will be obtained other than demographic characteristics and pain duration.

2.12 Data analysis:

Two sample t test will be used to compare the group at baseline to determine the sample characteristics in the both group will be statistically equal. To find out the significant variation in the group after the intervention again two sample t test will be used.

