2.13 Time Duration:

This study will be conducted from July 2022 to July 2024, for two years with three months data collection.

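### Disability is an objective, a formal hypothesis and a predicted result, but the plan collects no disability measure; the likely stand-in, the PSEQ, measures confidence and is never tied to Hypothesis 5

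*Combined protocol and SAP*

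**What the plan says.** Disability is promised in three places. Section 1.2 closes its five specific objectives with "To evaluate the effectiveness of thoracic mobility exercise and manual release technique in improving disability". Section 2.5 sets out Hypothesis 5 as a difference in means, with the null "There is no difference in disability of participants between experimental and control group" and a two-sided alternative. Section 3 groups disability with range of motion and strength as outcomes on which exercise is expected to do better.

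The sections on measurement do not mention it:

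- Section 2.8 says that assessors will "collect the demographic data, Pain assessment, Range of Motion and muscle strength at the baseline and after two weeks of intervention".
- Section 2.9 adds the PSEQ, described as "developed to assess the confidence people with ongoing pain have in performing activities while in pain". On the pain items it says that the "VAS scale will be used to measure the intensity of pain in different situations".
- Section 2.11 lists the outcomes, ending with "Muscle strength of thoracic spine extensors and overall scale of Pain-Self- efficacy Questionnaire", and takes the same set again at two weeks, apart from demographics and pain duration.
- Section 2.12 says only: "To find out the significant variation in the group after the intervention again two sample t test will be used". It names no variable.

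The word disability does not occur in sections 2.8 to 2.12 or in either Annex II questionnaire.

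**The concern.** A hypothesis about a difference in means needs a variable whose mean can be taken. Hypothesis 5 has none declared. Two readings of the plan are possible. On the first, disability was never going to be measured, so one specific objective and one hypothesis cannot be addressed. On the second, the PSEQ is silently standing in for disability, and a result about how confident participants feel would be published as a result about how limited they are.

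The two constructs can move separately. A participant may become more confident of coping while doing no more than before, or may do more without feeling more confident. The direction of scoring also differs: a higher PSEQ score is better, whereas more disability is worse, so the sign of any effect needs stating. A smaller point is that, with no variable declared, the one used for Hypothesis 5 could be settled after the data are seen.

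**Working it through.** The plan gives no figure on this point, so the check is a trace from hypotheses to measures, plus a simple count.

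**Step 1. Match each treatment hypothesis (2.5) to what is collected (2.9, 2.11, Annex II 5.2.2).**

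| Hypothesis | Construct | Measure in the plan | Variables at two weeks |
|---|---|---|---|
| 2 | Pain intensity | VAS, 0 to 10, in eight situations | 8 |
| 3 | Thoracic mobility | Tape-measured thoraco-lumbar flexion and extension | 2 |
| 4 | Extensor strength | Oxford grade | 1 |
| 5 | Disability | None stated | 0 |
| None | Pain self-efficacy | PSEQ overall score | 1 |

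The post-test variables total 8 + 2 + 1 + 1 = 12, and 0 of the 12 are identified as disability. Of the four treatment hypotheses (2 to 5), Hypothesis 5 is the only one whose construct matches no listed measure. In the other direction, self-efficacy appears in 0 of 5 specific objectives and 0 of 5 hypotheses, so the PSEQ is an outcome with no stated purpose.

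**Step 2. Test the two possible stand-ins against the plan's own descriptions.**

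- *PSEQ.* Section 2.9 defines it by confidence, and the instruction in both questionnaires asks how confident the participant is. All 10 items are answered from 0 (not at all confident) to 6 (completely confident), so a simple sum, which I assume is what section 2.11 means by the overall score, has a maximum of 10 × 6 = 60. On my reading of the printed items, four name a concrete activity (items 2, 3, 5 and 6: chores, socialising, work, hobbies), worth 4 × 6 = 24 points or 40%. Two concern coping only (items 4 and 7), worth 2 × 6 = 12 points or 20%. The other four (items 1, 8, 9 and 10) are general, worth 4 × 6 = 24 points or 40%. This grouping is a judgement and the conclusion does not depend on it. What counts is that every item is scored on confidence.
- *VAS rating for day-to-day activities.* This names activity, but section 2.9 says that the VAS scores the intensity of pain. It belongs to Hypothesis 2.

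**Step 3. Look for any sentence that makes the link.** Section 2.8 mentions neither disability nor the PSEQ. Section 2.11 lists the PSEQ under its own name. Section 2.12 assigns no variable to any hypothesis. Section 3 names a tool for pain but none for disability.

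**Step 4. Rule out missing text.** The outcome list and both questionnaires are present in the document, so pages removed before publication do not explain the gap.

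**The case against.** The best defence is that the intended mapping is plain. Section 2.9 gives the post-test form four sections and there are four treatment hypotheses. Once pain, range of motion and strength are paired off, the PSEQ is left for Hypothesis 5, and several of its items concern functioning. If items 9 and 10 (normal lifestyle, becoming more active) are counted as well, six of ten items have activity content, or 6 × 6 = 36 of 60 points. On this view the fault is one of labelling, in the last of five specific objectives, in a trial whose general objective is pain. It can also be said that section 2.12 names no variable for any hypothesis, that the omission from section 2.8 is only a summary left incomplete, and that little room remains for choosing a variable after the event.

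Much of this is fair. The PSEQ probably is the intended variable, the omission in 2.8 needs only a consistency edit, and the scope for post hoc choice is small. The documents cannot settle how closely PSEQ scores track disability. Two things remain. First, a reader should not have to infer which variable tests a formal hypothesis. The silence of section 2.12 does less harm for Hypotheses 2 to 4, because their constructs are recognisable in section 2.9 and disability is not. Second, if the inference is right, the label is still wrong by the protocol's own description: activity content in an item does not turn a confidence rating into a report of limitation.

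**Conclusion.** The concern holds. As written, the plan cannot support a conclusion on disability: no measure for it is collected at baseline or at two weeks, and the probable proxy measures something else and is not declared as one. The reach is one specific objective, one of four treatment hypotheses and one prediction in section 3. The comparisons of pain, range of motion and strength are not touched by this point.

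A disability claim drawn from the PSEQ would be unsupported and mislabelled; it would not necessarily be false. This should be fixed, but it does not threaten the trial as a whole. The finding itself rests only on the text. That the PSEQ is the intended proxy is an inference by elimination, and nothing in the verdict changes if another variable was meant.

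**What to change.** **Main route, before outcomes are analysed.** Issue a dated amendment and disclose it in the report:

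- In section 1.2 (last bullet), Hypothesis 5 and section 3, replace disability with pain self-efficacy, defined as the PSEQ total, 0 to 60, higher being better.
- Add the PSEQ to the list in section 2.8, so that it agrees with 2.9, 2.11 and the questionnaires.
- Name the PSEQ total in section 2.12 as the variable for Hypothesis 5.
- Draw no conclusion on disability.

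This costs a text change and no new data. Its drawback is that it alters a prespecified outcome label to fit the instrument, which is why the timing and the disclosure matter.

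**Alternative, only if data collection has not begun.** Add a short, validated, self-completed disability questionnaire at baseline and at two weeks, name it as the variable for Hypothesis 5, and keep the PSEQ as a separate outcome. The cost is one extra form at each of the two existing assessments. This route closes once baseline data have been taken.

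The document does not state where the trial stands; section 2.13 says only "This study will be conducted from July 2022 to July 2024, for two years with three months data collection". If analysis has already started, report Hypothesis 5 as not assessed and present the PSEQ result under its own name.

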2. DESIGN AND METHOD

2.1 Study Site:

Study will be conducted University of Peradeniya.

2.2 Study Population:

Undergraduates who are currently having upper back pain for more than seven days will be selected as sample. Participants who will have sub-acute and chronic pain which means who will have pain more than a week or seven days will be selected as sample and who have subjected to any recent surgeries, recent fractures, accidents or injuries in upper back will be excluded from the study.

2.3 Study Setting:

Study will be conducted in Service unit of Department of physiotherapy at University of Peradeniya.

2.4 Study Design:

This study is a Randomized Control Trial, Double- Blinded study. Participants and assessors will be blinded. Participants will be allocated randomly in to two groups which are experimental group which will receive thoracic mobility exercises and control group which will receive myofascial release and joint mobilization treatment.

2.5 Hypothesis:

1. Hypothesis about difference in baseline characteristics of participants between control and experimental groups

Null Hypothesis: $H_0: \mu_1 - \mu_2 = 0$

There is no difference in baseline characteristics of participants between experimental and control group.

Alternate Hypothesis: $H_1: \mu_1 - \mu_2 \neq 0$

There is a difference in baseline characteristics of participants between experimental and control group

2. Hypothesis about differences in pain intensity between control group and experimental group.

Null Hypothesis: $H_0: \mu_1 - \mu_2 = 0$

There is no difference in pain intensity of participants between experimental and control group.

Alternate Hypothesis: $H_1: \mu_1 - \mu_2 \neq 0$

There is a difference in pain intensity of participants between experimental and control group

3. Hypothesis about differences in thoracic mobility (Range of Motion) between control group and experimental group.

Null Hypothesis: $H_0: \mu_1 - \mu_2 = 0$

There is no difference in thoracic mobility of participants between experimental and control group.

Alternate Hypothesis: $H_1: \mu_1 - \mu_2 \neq 0$

There is a difference in thoracic mobility of participants between experimental and control group

4. Hypothesis about differences in muscle strength of spinal extensors between control group and experimental group.

Null Hypothesis: $H_0: \mu_1 - \mu_2 = 0$

There is no difference muscle strength of spinal extensors of participants between experimental and control group.

Alternate Hypothesis: $H_1: \mu_1 - \mu_2 \neq 0$

There is a difference in muscle strength of spinal extensors of participants between experimental and control group

5. Hypothesis about differences in disability of participants between control group and experimental group.

Null Hypothesis: $H_0: \mu_1 - \mu_2 = 0$

There is no difference in disability of participants between experimental and control group.

Alternate Hypothesis: $H1: \mu_1 - \mu_2 \neq 0$

There is a difference in disability of participants between experimental and control group.

2.6 Sample Size:

Sample size is Calculated by using G*power 3.1.9.4 software by assigning power 80% effective size 0.5, type I error = 0.05 and type II error = 0.2. Therefore calculated sample size was 42. Drop down rate of participants is assigned as 25 %. Therefore final sample size which obtained is 60 (Kang, 2021).

2.7 Sampling method:

Simple Random Sampling will be used as sampling technique as well as 30 Participants will be randomly allocated to each group. Participant will be allocated to the groups by using lottery method.

2.8 Data collection:

Undergraduates who are having upper back pain more than 7 days will be selected as sample and those who are having any contraindications, recent surgeries, fractures, accidents will be excluded from the students. Informed consent will be obtained from the participants. Participants will be allocated to one group by blindly select the number by lottery method. Thirty participants will be allocated randomly to each group. Allocation was concealed. Assessors will not be aware of intervention or control group and collect the demographic data, Pain assessment, Range of Motion and muscle strength at the baseline and after two weeks of intervention.

2.9 Data collection tool:

Measurement tool contains two sections such as pre-test and post-test questionnaire. In Pre-test questionnaire, there are six sections which includes personal details of the participants, pain related questions, Measurement of range of motion at base line, muscle strength at base line and pain-self-efficacy Questionnaire (PSEQ) at base line. In Post-test questionnaire, there are 4 sections which include, pain related questions

mainly pain intensity after two weeks, muscle strength after two weeks, Range of motion after two weeks and pain-self-efficacy Questionnaire (PSEQ).

Personal details of the participants will be collected separately for the concealed allocation and participants will be identified by code number. Participants' age, gender, height, weight, BMI, family size, bread winner of the family, monthly income and financial support for the study will be collected in the demographic data section. In third section, questions related to occurrence of pain, pain duration and treatments which were undertaken for the pain will be collected from the participants.

VAS scale will be used to measure the intensity of pain in different situations which include present pain intensity, in sitting, in forward bending, in standing, in walking, in sleeping, in transferring and during day to day activities. Visual Analogue Scale will be used to measure the pain intensity. Subjects will be asked to mark the number between 0 and 10 that fits best to their pain intensity. Zero indicates 'no pain at all' whereas 10 represents 'the worst pain ever possible' (Figure 1). Measurement will be obtained in the baseline and at the end of two weeks.

[figure not shown]

Figure 1- VAS Scale

Thoraco-Lumbar flexion and Extension of thoracic spine Range of Motion will be taken in the fourth section. Measurement will be taken by using measuring tape. Measurement will be taken at the baseline and after two weeks. In the fourth section, muscle strength of thoracic spine extensors will be measured using Oxford-Grading Scale. Measurement will be taken at the baseline and after two weeks. The Oxford Muscle Scale is a numerical rating scale used to quantify the power or strength produced by the contraction of a muscle. The scale was originally developed by a UK government research group called the Medical Research Council (MRC). Reliability of the scale

explained by Intraclass Correlation Coefficient (ICC) and Interrator Reliability. It shows high ICC coefficient of 0.95 (ranging from 0.92 to 0.97) (Hermans et al., 2012).

Muscle Strength Grading Scale (Oxford Scale)	
0/5	No Contraction
1/5	Visible/palpable muscle contraction but no movement
2/5	Movement with gravity eliminated
3/5	Movement against gravity only
4/5	Movement against gravity with some resistance
5/5	Movement against gravity with full resistance

Table 1

In the sixth section, The Pain Self-Efficacy Questionnaire (PSEQ) is a 10-item questionnaire developed to assess the confidence people with ongoing pain have in performing activities while in pain. The PSEQ has high internal consistency (0.92 Cronbach's alpha) and test-retest reliability is high of a 3-month period.

	0 "not at all confident"	1	2	3	4	5	6 "completely confident"
1. I can enjoy things, despite the pain.							
2. I can do most of the household chores (e.g. tidying-up, washing dishes, etc.), despite the pain.							
3. I can socialise with my friends or family members as often as I used to do, despite the pain.							

4. I can cope with my pain in most situations.						
5. I can do some form of work, despite the pain. ('work' includes housework, paid and unpaid work).						
6. I can still do many of the things I enjoy doing, such as hobbies or leisure activity, despite pain.						
7. I can cope with my pain without medication.						
8. I can still accomplish most of my goals in life, despite the pain.						
9. I can live a normal lifestyle, despite the pain.						
10. I can gradually become more active, despite the pain.						

Table 2

2.10 Ethical Considerations:

Ethical approval will be obtained from the Institutional Review Board of Bangladesh Health Professional Institute. Written informed consent will be obtained from all the subjects who are willing to participate in the study. Participation in this research is entirely voluntary basis and the participants have the right to withdraw from the study at any time.

2.11 Outcome measures:

Baseline outcome measures are demographic characteristics of participants such as age, gender, BMI, family size, bread winner of the family, monthly income and financial

support for study; Pain duration; Pain intensity at present moment, sitting, forward bending, standing, walking, sleeping, transferring and pain when performing day to day activities; Range of Motion of thoraco-lumbar flexion and extension; Muscle strength of thoracic spine extensors and overall scale of Pain-Self- efficacy Questionnaire. After two weeks same outcome measures will be obtained other than demographic characteristics and pain duration.

2.12 Data analysis:

Two sample t test will be used to compare the group at baseline to determine the sample characteristics in the both group will be statistically equal. To find out the significant variation in the group after the intervention again two sample t test will be used.

2.13 Time Duration:

This study will be conducted from July 2022 to July 2024, for two years with three months data collection.

